Morning: The participant will come to WARU or Trimsaran Community Health Centre at the pre-organised timeslot to allow the researchers to collect a fasted capillary (fingerpick) blood samples and stool sample (which may be brought in with the participant). The participant may consume their breakfast after the visit. The participant will also collect the allocated tea bags. The researcher will also take the participants the weight and height. The researcher will ask the participant to record their stool consistency using the Bristol stool scale and record their diet using the PDQS questionnaire.

Over 21 days: the researchers would like the participant to consume a cup of hot-infused tea after their last meal/snack of the day (post 6pm) daily, for 21 days. The researcher would ask the participant not to consume anything after the tea. In a cup/mug the researcher would ask the participant to place a 2.5g tea bag and add 190ml of hot water (80-100°C) and stir clockwise 10 consecutive times to allow for optimal infusion and then allow to brew for 5 minutes, before removal.

Whilst undergoing the experimental sessions, if necessary, the researcher will be easily contacted by email, Teams or phone.

GDPR: For the data the Welsh Government requires, Welsh Government is the data controller and Aberystwyth University (WARU) is the data processor. For any other data, including sensitive personal data, the data controller and the data processor is Aberystwyth University (WARU).

After the experimental period:

Morning of the final visit. Please come to WARU or Trimsaran Community Health Centre at the pre-organised timeslot to allow the researchers to collect a fasted capillary (fingerpick) blood samples and stool sample (this may be brought in with the participant). The researcher will also take the participants the weight and height. The researcher will ask the participant to record their stool consistency using the Bristol stool scale and record their diet using the PDQS questionnaire. The participant may consume their breakfast after their visit. Afterwards, the participant can go back to their 'normal' eating pattern.

Post study

The researcher would like the participant to fill in an additional PDQS questionnaire at least 21 days after the experimental period and provide their weight.

6) Participant Risks

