For the capillary blood samples, some people may feel nervous and on rare occasions dizziness may occur. Alongside green tea, the intervention teas may contain honeysuckle flower, Cassia seed, lotus leaf, five-leaf ginseng, hawthorn fruit, senna leaf and rhubarb root. The herbal teas contain low amount of caffeine and, if large quantities of the herbal teas are consumed in one go, a laxative effect may occur. The tea ingredients have already been tested for any adverse effects in a human cohort, however if any negative effects occur, participants are asked to refrain from continuing in the study.

7) Benefits to participant

There is no financial gain for participants if they decide to join this study. They will allow the researchers to gain important insight into the action of health teas using a combination of techniques including metabolomics, gut microbiome analysis and lipid analysis. This will be the first time this type of research will have been conducted and will be a valuable pilot study before they can investigate any human health benefits in the future. Researchers will provide participants with tea for the experimental days.

8) Privacy/confidentiality

Participants are informed that only the researchers involved with the study will be able to look at the information they provide. Specific details and personal identifiers will only be available to the researchers. At the end of the study, any information relating to participants will be made pseudonymous (coded without their name associated). Participants will not be identifiable in any publication that may arise from this research. Electronic files will be kept in a logical manner and will always be kept grouped within specific folders and password protected. All data storage is using the AU network and backed up. Once the raw data has been extracted from a paper version onto a computer, the paper will be destroyed via a paper shredder or in confidential waste bags to ensure the participant's confidentiality. There may be times when keeping paper forms are necessary (consent forms), but in this case the paper versions will be kept in a locked filing cabinet. All files that are stored on the WARU share drive will always be protected with a secure password. Setting passwords will automatically encrypt the document and will not allow any unauthorised access to the data. The Gatekeeper of the passwords delivers the passwords by encrypted emails. When sharing

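### Section 8 has paper data records destroyed once their content is on a computer, with no prior check against source and no retention period stated

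*Protocol*

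**What the plan says.** The rule is in Section 8, on privacy and confidentiality: "Once the raw data has been extracted from a paper version onto a computer, the paper will be destroyed via a paper shredder". Disposal as confidential waste is given as the alternative. The reason given is confidentiality alone.

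An exception follows: "There may be times when keeping paper forms are necessary (consent forms"), in which case "the paper versions will be kept in a locked filing cabinet". Consent forms are the only example.

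The same section says of electronic files: "All data storage is using the AU network and backed up".

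The data most likely to start on paper are described in Section 5.6. At the baseline and final visits the participant is asked to "record their stool consistency using the Bristol stool scale and record their diet using the PDQS questionnaire". On body size the text is: "The researcher will also take the participants the weight and height". After the study the participant is to "fill in an additional PDQS questionnaire at least 21 days after the experimental period and provide their weight". The protocol does not say whether any of these items is captured on paper or electronically.

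**The concern.** Destroying source records cannot be undone, and here the only stated trigger is that the data have reached a computer. If a value later looks implausible, there is no form left to consult. The analyst can keep it or remove it by judgement, but cannot restore it. A weight or stool score from the final visit cannot be measured again for that date.

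The data concerned have a purpose in this trial. Weight control is part of the statement of purpose in Section 2. Section 5.1 gives the diet score a directional hypothesis, uses stool form to watch for laxative effects, and plans to correlate weight and BMI with the microbiome. With 55 participants in three arms, a single gross error is not averaged away.

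A statistical analysis plan written later could not repair this, because the forms would already be gone.

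**Working it through.** The protocol gives no figure to reproduce on this point. The check is a reading of the data-handling text, followed by arithmetic for scale.

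**1. Is there any safeguard before destruction?**

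| Place in protocol | What it covers | Check or retention of data forms? |
|---|---|---|
| Section 8 | Destruction rule, paper exception, passwords, shared drive, back-up | None stated; the exception names only consent forms |
| Section 9.2 | Computer access, back-up, ID codes, room access | None stated |
| Section 9.3 | Where laboratory and data analysis take place | None stated |

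Back-up protects against loss of the electronic file. It would preserve a wrong entry as faithfully as a right one.

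**2. Does confidentiality require early destruction?** Section 8 already provides a locked cabinet. Section 9.2 provides card-key rooms and ID codes that only the gatekeeper can link to names. Coded forms held under those arrangements would serve the same aim.

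**3. Which data are exposed?** Section 5.6 names four items at each of two visits (diet questionnaire, stool score, weight, height) and two items post-study (diet questionnaire, weight). With 55 participants (Section 5.2):

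55 × (4 + 4 + 2) = 550 records.

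This is an upper figure. It assumes that every item is first recorded on paper and that participation is complete. The primary-objective lipids are outside it: Section 9.3 sends them to a hospital laboratory.

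**4. How many errors?** The documents cannot say. Two illustrations show how far the answer depends on assumptions. Both use an assumed error rate of 0.5% to 1%.

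- Counting records: 550 × 0.005 = 2.75 to 550 × 0.01 = 5.5.
- Counting fields, with an assumed 20 to 30 per participant per visit over two visits: 55 × 2 × 20 = 2,200 to 55 × 2 × 30 = 3,300 fields, giving 2,200 × 0.005 = 11 to 3,300 × 0.01 = 33.

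These count errors made at entry. How many would stay uncorrected depends on checking that the protocol does not describe.

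**5. What could one error do?** Assume equal arms (55 / 3 ≈ 18), a true SD of weight change of 1.5 kg, and one weight wrong by 10 kg.

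- Shift in the arm's mean change: 10 / 18 = 0.56 kg.
- Expected sample variance: 1.5² + 10² / 18 = 2.25 + 5.56 = 7.81, so the SD is √7.81 ≈ 2.8 kg.
- If the value is dropped instead: 1 / 18 = 5.6% of the arm's data for that measure.

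The arm size, SD and size of slip are assumptions, not protocol figures.

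**The case against.** The strongest reply is that half of the point rests on silence. Section 8 says that paper is destroyed after extraction; it does not say that extraction is unchecked. Entry checks often sit in a data-management plan or unit procedure, which is not at hand. The sentence is in a privacy section and is not written as a data-entry workflow. Nor does extraction have to mean typing: a scan would leave an image, although none is described. All of this stands, so the point can say only that no check is stated.

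The paper exception is also worded openly, and could be read to allow data forms to be kept. That softens the rule, but the protocol commits to keeping nothing beyond its one example.

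Three stronger readings are tempting, and the documents do not support them.

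- **The primary result is at risk.** The lipids come from a hospital laboratory and are not shown to depend on these forms.
- **The rule creates bias between arms.** Section 5.6 makes the trial double blind, so entry errors should be unrelated to arm and act mainly as noise. Nothing in the text suggests that outliers would be judged after unblinding.
- **Errors would pass unseen.** Each participant has up to three weights and two heights, so a 10 kg slip would probably be noticed. What is lost is the ability to recover the recorded value from source.

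**Conclusion.** The point holds as a modest one about data handling. The protocol fixes an irreversible step, gives extraction as its only condition, and states no verification, scan, database lock or retention period before it. For whatever is first recorded on paper, later correction from source would be impossible.

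The conclusion rests on two inferences: that the diet score, stool form, weight and height are captured at least partly on paper, and that no unseen procedure already requires a check. If both hold, the exposure is up to 550 records of secondary and exploratory data, with some loss of precision and auditability as the likely effect. The error counts and the weight example show scale only and should not be quoted as estimates. The protocol calls the work a pilot (Section 7), which also argues for a low rating. Label: cheap improvement, low severity.

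**What to change.** Replace the trigger in Section 8 with wording such as: *Paper data forms, identified by ID code only, or verified scans of them, are kept in the locked filing cabinet (scans on the secured drive) until all entries have been checked against source and the database is locked. They are then destroyed after the applicable retention period.* State the length of that period, and say which items are captured on paper.

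If a check already exists in a unit procedure, a reference to it in Section 8, with destruction made conditional on its completion, would supply the verification step.

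The cost is a short text change, cabinet space and a few hours of checking for 55 participants. The drawback is that coded paper is held for longer, under locks and access controls that the protocol already describes. The change helps only for forms not yet destroyed, so it should be made before any are shredded.
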